## Objective 5:

[figure not shown]
We will describe the number and proportion of patients that follow different treatment strategies in the 180 days following the end of treatment. These strategies are defined as:

- Restart the same treatment
- Switch to a different treatment
- Restart and switch to a different treatment
   Discontinued treatment (not treated, neither with the original treatment nor any potential switch)

For this objective (time period comparison), both incident and prevalent users will be considered. The proportion of individuals following each treatment strategy (e.g. switching) will be calculated using the number of people exposed to the product of interest during the time period under study (e.g. pre-intervention) as the denominator regardless of when the initiation started.

Figure 2 illustrates some of these scenarios.

**Figure 2.** Outcomes after the drug exposure of interest (in blue) over different time periods.

Source: DrugUtilisation R package website (22)

The number of meningioma cases occurring any time during treatment with NOMAC or CMA, and in the six months prior to the end of treatment will also be reported. For cases identified in the six months prior, we will report the treatment strategy followed after treatment (i.e. restart, switch, both, or discontinuation).

NOMAC and CMA will be assessed separately. Results will be reported overall and stratified by study period (pre- vs. postintervention) and WHO 5th ATC level codes (if counts allow). For the pre- and post-intervention comparison, treatments initiated during the 180 days before the intervention will not be considered, to ensure sufficient time for assessing outcomes (e.g., switches, discontinuations) prior to the intervention.

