#### **Outcomes**

- Objective 1: Prescribing of drug classes or progestogens of interest (assessed separately)
- Objective 2: N/A (treatment duration and cumulative use of exposures)
- Objective 3: N/A (characterisation)
- Objective 4: Prescribing of alternative drug classes of interest not containing NOMAC or CMA
- Objective 5: Number of meningioma cases during treatment. Discontinuations or switches to alternative drug classes of interest not containing NOMAC or CMA.
- Objective 6: Prescribing of NOMAC or CMA.

Authors: [name], [name], [name], [name], [name]

Version: V4.0

Dissemination level: Public

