#### Objective 5:

We will describe the frequency of switches of treatment with NOMAC or CMA to products of other relevant drug classes not containing NOMAC or CMA within 180 days after the end of treatment. We will also describe the number of patients discontinuing treatment. The number of meningioma cases occurring any time during treatment with NOMAC or CMA, and in the six months prior to treatment discontinuation will also be reported. Exposures of interest (NOMAC vs. CMA) will be assessed separately.

Results will be reported overall and stratified by study period and WHO 5th ATC level codes (if counts allow).

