In July 2022, PRAC issued further recommendations for both NOMAC and CMA. PRAC recommended to update the summary of product characteristics for products containing NOMAC or CMA to inform of the risk of meningioma. PRAC recommended that medicines containing high-dose chlormadinone (5 – 10 mg) or high-dose NOMAC (3.75 – 5 mg) should be used at the lowest effective dose and for the shortest duration possible. These medications should only be used when other interventions are not appropriate and should no longer be considered for first-line treatment. Similar to what was already established for NOMAC, treatment with products containing NOMAC or CMA was contraindicated in patients with current or prior history of meningioma. PRAC also recommended monitoring patients for symptoms, and permanently discontinuing treatment if the patients develop meningioma. (9) Measures recommended by PRAC were endorsed by the Committee for Medicinal Products for Human Use (CHMP) and the European Commission issued final legally binding decisions applicable in all the European Union (EU) Member States, between 28th of October and 28th November 2022.(10) Following this decision, a direct healthcare professional communication (DHPC) was sent to prescribers (8th November 2022)(11) and Marketing Authorisation Holders (MAH) had one month to implement changes (28th December 2022). Dates for national-level interventions varied, especially in the case of France, where additional interventions were put in place between 2018 and 2021.

The overall aim of the study is to describe how prescribing of NOMAC and CMA has changed following the introduction of risk minimisation measures (RMM) in November 2022. To contextualise findings, it is also of interest to study changes in prescribing of other relevant drug classes, including progestogen and oestrogen combination products and progestogens that are pregnadien derivatives, and to study the impact of prior EU-level restrictions in trends of NOMAC prescribing.

D2 C	2 000	Charles	Donate and
P3-C.	3-UU6	Stuav	Protocol

Version: V4.0

**Dissemination level:** Public

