	
 
Progestogens that are pregnadien derivates (including medroxyprogesterone and medroxyprogesterone alone)
 

	- Progestogen and oestrogen combination products.
	Objective 4: Same as Objective 2.
	Objective 5: Same as Objective 2.
	Objective 6: N/A
Comparator:	Before vs. After the implementation of restrictions
Outcome:	Objective 1: Prescribing of drug classes of interest (assessed separately)
	Objective 2: N/A (treatment duration and cumulative use of the exposure).
	Objective 3: N/A (characterisation of users)
	Objective 4: Prescribing of alternative treatments not containing NOMAC or CMA (assessed retrospectively to identify line of treatment).
	Objective 5: Number of patients diagnosed with meningioma during treatment and number of patients discontinuing treatment or switching to alternative treatments not containing NOMAC or CMA 180 days after the end of the index treatment.
	Objective 6: Prescribing of products containing NOMAC or CMA (assessed separately).
Time:	01/01/2010 to end of data availability
Setting:	Routinely collected data from 3 databases in 3 European countries.
Main measure of effect:	Objective 1:
	Incidence rates (new prescriptions per 100,000 person-years of the population at risk) and prevalence (proportions).
	Objective 2 to 5:
	- Objective 2: Median with minimum, maximum and interquartile range.
	- Objective 3-5: Counts and proportions
	
 
All objectives: Standardised Mean Differences (SMD) for comparing changes before and after the implementation of restrictions.
 

	Objective 6:
	Risk ratios derived from the interrupted time series analysis (ITS). ITS will be based on results obtained as part of Objective 1.

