Prior database history	Study participants with less than 365 days of prior history observed at index date will be excluded	After	[-365, -1]	IP, OP	N/A	N/A	All except general population (objective 1 and 6)
Prior use of NOMAC	Individuals with prior prescriptions of NOMAC will be excluded	After	[-Inf, -1]	IP, OP	N/A	N/A	New users of NOMAC (objective 2, 4 and 5)
Prior use of CMA	Individuals with prior prescriptions of CMA will be excluded	After	[-Inf, -1]	IP, OP	N/A	N/A	New users of CMA (objective 2, 4 and 5)

<sup>2 IP = inpatient, OP = outpatient

<sup>3 Specify whether a diagnosis code is required to be in the primary position (main reason for encounter)

Authors: [name], [name], [name], [name], [name]

Version: V4.0

**Dissemination level:** Public

Prior use of	Individuals with prior	After	[-Inf, -1]	IP, OP	N/A	N/A	New users of
drug classes	prescriptions of any of the						drug classes
of interest	drug classes of interest will be						or
(any)	excluded						progestogens
							of interest
							(objective 3)

<sup>1 Relative to the study entry date

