#### Objective 4:

For each participant initiating treatment with NOMAC or CMA, we will retrospectively assess the occurrence of records indicating the use of other drug classes of interest not containing NOMAC or CMA. This assessment will be performed from the day before index date to the earliest of the start of the study period or the start of the observation period for each patient. We will describe the order in which treatments of interest were prescribed, as first vs. non-first treatments. NOMAC and CMA will be assessed separately.

NOMAC and CMA will be assessed separately. Results will be reported overall and stratified by study period (pre- vs. postintervention), dose (high- vs. low-dose products), and indication (non-HRT vs. HRT). Dose and indication will be assessed at index date (i.e. date of treatment initiation with NOMAC or CMA). Please see "11. Limitations" for more information.

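### Objective 5 reports a woman who moves only between NOMAC and CMA as discontinued and not treated, and Objective 4 can class her second restricted substance as first-line

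*Protocol*

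**What the plan says.** **Switch targets.** The Abstract (Outcomes) gives the Objective 5 outcome as "Discontinuations or switches to alternative drug classes of interest not containing NOMAC or CMA". The Abstract text on Objective 5 counts switches "to products of other relevant drug classes not containing NOMAC or CMA within 180 days after the end of treatment". Table 1 agrees: "switching to alternative treatments not containing NOMAC or CMA 180 days after the end of the index treatment". Section 8.6.2 and Table 8 carry the same restriction, and Appendix I puts it into code lists.

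**Strategies after treatment.** Section 8.8, Objective 5, lists four: restart, switch, both, and a remainder worded "Discontinued treatment (not treated, neither with the original treatment nor any potential switch". NOMAC and CMA are assessed separately, so a restart means the index substance. For meningioma cases found in the six months before the end of treatment, the same four strategies are reported.

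**Line of treatment.** For Objective 4, section 8.8 states that "we will retrospectively assess the occurrence of records indicating the use of other drug classes of interest not containing NOMAC or CMA". Table 6 excludes prior use of the same substance only; for the CMA cohort, "Individuals with prior prescriptions of CMA will be excluded". The NOMAC row mirrors this.

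**The measures.** Section 6 says of 2022 that "treatment with products containing NOMAC or CMA was contraindicated in patients with current or prior history of meningioma".

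**The concern.** The 2022 measures apply to both substances. A woman moved from one to the other has not left the restricted pair, yet no Objective 5 category can hold her except the one described as not treated. The category's label is then false for her.

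Three results are affected:

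- The proportion discontinuing, which is compared before and after the measures by a standardised mean difference separate from the one for switching.
- The strategy reported for women with meningioma. Section 6 describes either substance as contraindicated for them, and a move to the other one would appear as stopping.
- The first versus non-first split in Objective 4. A former CMA user can enter the NOMAC new-user cohort as first-line, and the reverse, although another restricted substance came before.

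**Working it through.** No figure in the protocol has to be reproduced. The check is whether the written rules lead where claimed.

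**Step 1: the code lists.** Section 8.6.3 gives three NOMAC codes (G03AA14, G03DB04, G03FB12) and four CMA codes (G03AA15, G03AB07, G03DB06, G03FB03), so 3 + 4 = 7. For Objectives 4 and 5, Appendix I removes five from the combination group (G03AA14, G03AA15, G03AB07, G03FB12, G03FB03) and two from the pregnadien group (G03DB04, G03DB06), so 5 + 2 = 7. No code of either substance remains as a switch target or as a prior line.

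**Step 2: the rules.** In the 180 days after the end of treatment, let R mean that the index substance is recorded again, and S that a listed alternative is recorded. R and S gives restart and switch; R alone gives restart; S alone gives switch; neither gives discontinued. In Objective 4, a start is first-line if no listed alternative is on record before the index date.

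**Step 3: example histories.** The Objective 5 column classifies the end of the first restricted substance. The Objective 4 column classifies the start of the second.

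| History | Objective 5 as written | Objective 4 as written |
|---|---|---|
| NOMAC, then CMA, nothing else | discontinued | first |
| CMA, then NOMAC, nothing else | discontinued | first |
| Listed alternative, then NOMAC, then CMA | discontinued | non-first |
| NOMAC, then CMA and a listed alternative within 180 days | switch | not examined |

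The discontinued label thus needs no restart and no listed alternative within 180 days. The first-line label needs no earlier record of a listed alternative. A plain move between the two substances meets both conditions.

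**Step 4: whether another analysis recovers her.** Objective 3 lists NOMAC and CMA among the medications described, but its population excludes prior use of any drug class of interest (Table 6), so an earlier course of the other substance cannot appear. Objectives 1 and 6 count her as a new user of the second substance if she has no recent use of it, but do not connect this to the first. Section 11 discusses line of treatment without mentioning the case.

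**Step 5: size.** Let D be the true share with no product in the 180 days, and c the share who move only to the other restricted substance. Then

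reported discontinuation = D + c.

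The documents give neither D nor c. With an assumed D of 40%, c = 1%, 5% or 10% gives 41%, 45% or 50%. The error is c whatever D is. For the comparison over time,

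reported change = (D_post − D_pre) + (c_post − c_pre).

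If c is stable, the difference in proportions is unaffected and only the two levels are wrong. The documents do not say whether c rises or falls.

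**The case against.** **The remainder may be read generously.** The second strategy in section 8.8 names no exclusion, so the other restricted substance could pass as a different treatment. That reading conflicts with the Abstract, Table 1, section 8.6.2, Table 8 and Appendix I, so the text needs correction either way.

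**Objective 4 may be deliberate.** Section 6 says that high-dose products are for use when other interventions are not appropriate. The look-back can reasonably ask whether an unrestricted alternative came first, and for a woman who had only CMA before NOMAC the answer is no. This stands. Counting the other restricted substance as an ordinary prior line would let one restricted product serve as the alternative to the other. What remains is that the plan does not show her separately.

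**The exposure is not hidden from the whole study.** The Objective 1 subgroup with prior meningioma reports NOMAC and CMA separately with a substance-specific washout, so a later CMA start can be counted there. This is correct at population level. It does not mend the individual strategy in Objective 5.

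**Such moves may be few.** Table 3 sets loose ceilings in some directions: 16.8k / 173.9k = 9.7% of German CMA users and 1.9k / 15.3k = 12.4% of Croatian CMA users could ever have moved to NOMAC. These are ever-user counts without restriction on age, sex or period. They show no overlap between the two groups, and they do not bound moves from NOMAC to CMA in those countries. They bound the problem but do not measure it.

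**A reader might infer that dose reduction is never visible.** The documents do not support this. Objectives 1 and 6 are stratified by high and low dose, Objective 2 reports cumulative dose, and Table 11 lists dose as an Objective 5 subgroup. Only the individual move from a high-dose to a low-dose product has no outcome of its own.

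**Conclusion.** The point holds as a defect of definition. As written, Objective 5 labels a woman who moves only between NOMAC and CMA as discontinued and not treated, including in the report after meningioma. Objective 4 classes her second substance as first-line when no listed alternative is on record. Both follow from the protocol's own rules and code lists without further assumption.

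The size cannot be derived. Reported discontinuation is too high by c percentage points, and c is unknown. A reader might infer that the error pushes Objective 5 towards its hypothesis of more discontinuations. The documents do not support that: they give no pre- or post-intervention rate, both substances were restricted together in 2022, and NOMAC carried its contraindication earlier, so moves from NOMAC to CMA before 2022 are also plausible. Objective 5 is descriptive, without a formal test or pooling. The correction is nevertheless needed before the Objective 4 and 5 results are interpreted.

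**What to change.** In Objective 5, add a category for a move to the other restricted substance (NOMAC to CMA, CMA to NOMAC) and use it in the meningioma report as well. Define discontinuation as no NOMAC, no CMA and no listed alternative in the 180 days. State how a woman with both the other restricted substance and a listed alternative in that window is counted. Align the Abstract, Table 1, section 8.6.2, Table 8, section 8.8 and Appendix I.

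In Objective 4, report prior use of the other restricted substance, with no listed alternative on record, as its own category, merged into neither first nor non-first.

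The cost is small: the NOMAC and CMA code lists already exist, and each objective gains one result row. Cells become somewhat smaller, and some, most likely among meningioma cases, may fall below the reporting minimum of 5.

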#### 6. RATIONALE AND BACKGROUND

Medicines containing nomegestrol acetate (NOMAC) or chlormadinone acetate (CMA) are synthetic progestins with antiandrogenic effects. Approved indications for NOMAC and CMA in monotherapy or in combination with oestrogens differ between different strengths and different countries. In general, they are indicated for gynaecological and menstrual disorders, hormone replacement therapy (HRT) and, at lower doses, as hormonal contraception.

Meningioma is a rare tumour that forms from the meninges. Known risk factors for meningioma are being female, exposure to ionising radiation and neurofibromatosis type 2.(1) Recently published studies have found a dose-dependent association between NOMAC or CMA and meningioma.(2-5) The hazard ratio (HR) of intracranial meningioma adjusted for age was 4.5 (3.5-5.7) and 4.4 (95% CI 3.4-5.8) among women exposed to NOMAC and CMA, respectively.(2, 3) The risk of meningioma increased with dose and duration of treatment and diminished one year after the discontinuation of treatment. Prolonged exposure to progestogens other than NOMAC such as cyproterone acetate (6) and medroxyprogesterone acetate (7) has also been linked to an increased risk of meningioma.

The risk of meningioma associated with NOMAC is known since 2018 and has been assessed within different regulatory procedures.(8) In October 2018, the Pharmacovigilance Risk Assessment Committee (PRAC) recommended to amend the product information of monotherapy products containing NOMAC to include the contraindication for patients who have, or have had, meningioma. PRAC also recommended permanently discontinuing treatment in patients who develop meningioma. In 2020, the product information of products containing NOMAC in combination with oestradiol was updated with similar contraindications and warnings.

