## 8.4 Follow-up

For the population-level DUS (objective 1), study participants in the denominator population will start contributing person time on the latest of the following: 1) study start date (1st January 2010, or as defined according to the database), 2) date on which they turn 10 years old, 3) date at which they have a year of prior history recorded. Participants will stop contributing person time at the earliest date of the following: 1) end of available data in each of the data sources, 2) date at which their observation period ends (e.g. loss to follow-up, death).

For the patient-level DUS (objective 2 to 5), participants will be followed up from the day of incident prescription of medication (index date), until the earliest end of data availability, date at which their observation period ends (e.g. loss to follow-up, death), or 180 days after ending treatment (objective 5). For objective 2, 4 and 5, index date will be defined as the date of the first-ever prescription of NOMAC or CMA. For objective 3, this will be defined as the date of the first-ever prescription of any of the 6 drug classes of interest (see "8.6.2 Outcomes").

For objective 4, line of treatment will be assessed retrospectively by looking at prior records of alternative treatments, from the date of initiation of treatment with products containing NOMAC or CMA to start of the study period (1st January 2010, or as defined according to the database).

For objective 6, follow-up will be the same as that for objective 1.

Information on the operational definition of index date is described in **Table 4**. Please note that, for objectives 1 and 6, each drug class of interest will be assessed separately, with the washout window specific to the drug class being studied (e.g., when studying NOMAC, the washout window will be applied with respect to this substance only). For objective 3, the washout will be applied to all the drug classes of interest combined.

Authors: [name], [name], [name], [name], [name]

Version: V4.0

**Dissemination level:** Public

Table 4. Operational definition of time 0 (index date) and other primary time anchors.

Study population names	Time Anchor Description (e.g. time 0) 	Number of entries 	Type of entry	Washout window	Care Setting 	Code Type 	Incident with respect to

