#### Objective 2-5:

For objectives 2 to 5, SMD of each of the covariates for the comparison of drug users in the pre-RMM and post-RMM period as a measure of the impact of the profile of drug users. These covariates will include: duration and cumulative dose (objective 2), patient characteristics (objective 3) and line of treatment (objective 4). For patient characteristics, only conditions will be compared, with the assessment window set as any time prior to 1 day before the index date. For objective 5, covariates will include the proportion of patients diagnosed with meningioma during treatment, and the proportion of patients who discontinue or switch to alternative treatments (assessed separately).

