#### **Databases:**

In IQVIA LPD Belgium and IQVIA DA Germany, the observation period of the patients in these databases is calculated based on the last visit, observation or interaction of the patient with the health care system. This methodology impacts the individuals considered "at risk" for the different medicines of interest of the study (i.e., the individuals included in the denominator populations) during the latest months of available data from the latest data lock, where healthy and/or non-frequent users of the health care system will not be considered active. Consequently, the denominators that will be used to calculate the incident use of drugs in the population may present an artefactual decrease whilst the incident users will remain, incrementing the incidence and prevalence ratios. The presence of these artefacts will be considered when interpreting the results. However, this is likely to affect the amount of follow up available for the study. We expect that the data from the last 6 months may not accurately reflect actual figures of use and, therefore, will be excluded from the analysis for Objective 1 and 6.

Regarding the study period, NAJS will provide data from 2017 onwards only, as prior data might include information on duplicated patients. IQVIA LPD Belgium will provide data from 2012 onwards.

Since information on drug exposure end dates is unavailable in NAJS, treatment duration will not be inferred directly from the start and end dates of drug exposure. Instead, we will infer the treatment period using only the drug exposure start dates, assuming continuous drug exposure between consecutive start dates, if separated by less than 90 days. To account for the final prescription, we apply a 30-day window following the last recorded drug start date. This approach might lead to some uncertainty regarding the exact duration or cumulative dose prescribed.

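### In NAJS, a meningioma diagnosed 31 to 89 days after a prescription start counts as during treatment if the woman continues and is missed if she stops

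*Protocol*

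**What the plan says.** Section 8.8, Objective 5, of the protocol defines two meningioma counts: "The number of meningioma cases occurring any time during treatment with NOMAC or CMA, and in the six months prior to the end of treatment". For cases in the six-month window it also reports what followed: restart, switch, both, or discontinuation. Section 8.8, Objective 2-5, then compares "the proportion of patients diagnosed with meningioma during treatment" before and after the measure by a standardised mean difference.

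Section 11, Databases, sets the end of treatment for the Croatian source: "Since information on drug exposure end dates is unavailable in NAJS", the treatment period is built from start dates alone, "assuming continuous drug exposure between consecutive start dates, if separated by less than 90 days". For the final prescription, "we apply a 30-day window following the last recorded drug start date". The only consequence it admits is uncertainty about duration and cumulative dose.

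Two other places matter. Section 6 records that the regulator recommended "permanently discontinuing treatment if the patients develop meningioma". Section 8.4 follows women for Objective 5 until 180 days after treatment end, but no section counts a meningioma diagnosed in those 180 days.

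**The concern.** The NAJS rule has two lengths. After a start that is followed by another in under 90 days, every day up to the next start is exposed, so up to 89 days. After a start that is followed by none, only 30 days are exposed. Whether a diagnosis between those limits falls during treatment is therefore decided by what the woman does after the diagnosis.

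That later behaviour is what the measure tries to change. The error is therefore not random: the better the advice to stop is followed, the fewer cases are counted, even if meningioma is as frequent as before.

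The six-month subset is affected in the same way. A woman who stops on diagnosis at day 45 has an inferred treatment end at day 30. Her diagnosis lies after that end, and she drops out of the table showing what happened after diagnosis. That table then leans towards women who took at least one more prescription.

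NAJS is not a marginal source here. Table 3 shows it as the only one of the three databases that includes hospital care, with 15.3k CMA users and 1.9k NOMAC users.

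**Working it through.** The protocol gives no figure for this point, so there is nothing to reproduce. The check applies the stated rule literally.

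**Inputs.** The joining limit (under 90 days) and the tail (30 days) come from section 11. The counting window (during treatment) comes from section 8.8, Objective 5. The NAJS refill interval L is not given, so a range of 28 to 98 days is assumed. Diagnosis is assumed uniform over the interval.

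**Step 1: which days are affected.** Let d be the days from the latest start to diagnosis.

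- d = 1 to 30: counted whether she continues or stops.
- d = 31 to 89: counted if the next start comes in under 90 days, missed if there is none.
- Gap of 90 days or more: not bridged, so a diagnosis after day 30 is missed in both cases.

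**Step 2: share of cases missed on stopping.** For L from 30 to 89 days, L days count if she continues and 30 if she stops, so the share missed is (L-30)/L.

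| Refill interval L (days) | Days counted if she continues | Days counted if she stops | Share missed on stopping |
|---|---|---|---|
| 28 | 28 | 28 | 0% |
| 30 | 30 | 30 | 0% |
| 56 | 56 | 30 | 26/56 = 46% |
| 60 | 60 | 30 | 30/60 = 50% |
| 84 | 84 | 30 | 54/84 = 64% |
| 89 | 89 | 30 | 59/89 = 66% |
| 90 | 30 | 30 | 0% |
| 98 | 30 | 30 | 0% |

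**Step 3: what this could do to a pre/post comparison (illustration, all inputs assumed).** Take 84-day refills and 100 true cases in each period, with a proportion p of women stopping at diagnosis. Counted cases = 100 × [(1-p) + p × 30/84].

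- p rises from 20% to 80%: 80 + 20 × 0.357 = 87 falls to 20 + 80 × 0.357 = 49, ratio 0.56.
- p rises from 50% to 90%: 50 + 50 × 0.357 = 68 falls to 10 + 90 × 0.357 = 42, ratio 0.62.

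True occurrence is the same in both periods.

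**Step 4: does a fixed window remove the dependence?** Under a rule that counts any diagnosis within 89 days after any start, d = 1 to 89 is counted whether or not a later prescription exists. Every case counted now stays counted, because a bridged gap never exceeds 89 days and the tail is 30.

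**The case against.** **The effect may not exist in these data.** With monthly refills it is nil, and it is nil again once gaps reach 90 days. This stands and limits the size. It does not remove the defect, because the protocol gives no refill interval that would rule out the range between.

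**Counting during treatment is the stated objective.** Sections 3 and 7 both define it so. This stands. A reader might infer from section 6, "The risk of meningioma increased with dose and duration of treatment and diminished one year after the discontinuation of treatment", that the count should run for a year after stopping and that the pre/post comparison should rest on that longer window. The documents do not support this: the objective describes diagnoses on treatment and what follows them, not attributable risk. The data would not carry it either. Table 3 gives data locks of 17-11-2023 (NAJS) and 30-09-2023 (Germany), so 180 days are complete only for treatments ending by about 21 May and 3 April 2023. A comparison on treatment plus 180 days would be truncated mainly in the post-period, and 365 days would be complete for no post-period treatment in either source.

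**The same fault in the IQVIA databases.** A reader might infer it from the rule in section 8.8, Objective 2, that joins eras less than 30 days apart. That rule is stated for cumulative dose, and duration there comes from recorded prescription start and end. Only NAJS lacks end dates.

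**Few cases, and no hypothesis on this proportion.** The Objective 5 hypothesis concerns switches and discontinuations. Section 11 puts meningioma counts in the hundreds for most databases, and counts under 5 are suppressed. As a rough order of magnitude, assume 300 NAJS cases, half of the 2.68M subjects female, 17.2k users (1.9k + 15.3k, or 1.28% of women), a hazard ratio of 4.5, and 9.5 post-period months out of 82.5. Then 300 × 0.0128 × 4.5 × 9.5/82.5 gives about 2 post-period cases among users (0.7 with 100 cases, 6 with 900). This stands: no counting window will make the pre/post contrast informative on its own. It also means that losing one or two cases can empty a cell.

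**The direction is not certain.** Section 6 also reports a recommendation to monitor for symptoms, which could bring diagnoses forward into treatment. For NOMAC, advice to stop dates from 2018 for monotherapy, with similar warnings for the oestradiol combination in 2020. This stands as a caution against predicting the net change.

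**Conclusion.** The point holds for NAJS. A diagnosis 31 to 89 days after a start is counted or missed according to whether the woman takes another prescription, and stopping is the recommended response to that diagnosis. The share missed on stopping runs from 0% at 30-day refills to 66% at 89-day refills and is zero outside that range. It rests on an assumed interval and uniform timing of diagnosis. The same cases drop out of the six-month subset, so the reported strategy after diagnosis leans towards women who continued. Section 11 does not disclose this.

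A reader might conclude that every NAJS case diagnosed between prescriptions is lost on stopping, or that any fall in the proportion after 2022 must be an artefact. Neither follows: the first 30 days are counted either way, and the net direction of change is open. With so few cases, the practical harm lies more in a skewed description of what followed diagnosis than in a wrong formal conclusion. The repair is cheap enough to be worth making.

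**What to change.** 1. **NAJS meningioma count only** (section 8.8, Objective 5): also count any meningioma diagnosed within 89 days after any NOMAC or CMA start, whether or not a later prescription exists. Use this window for the NAJS pre/post proportion, shown beside the count as now defined. Report the treatment strategy that followed for the added cases too.
2. **All databases:** add a separate descriptive count of first meningioma diagnoses from the day after treatment end to day 180, with the number of women whose 180-day follow-up is complete. Do not base the pre/post comparison on it.
3. **Section 11, Databases:** state that the NAJS end-of-treatment rule affects the meningioma counts as well as duration and cumulative dose, and report the observed distribution of gaps between starts so that readers can judge the size.

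The cost is protocol wording and two extra windows in the code; no new data are needed. The downside is that some diagnoses made after true stopping will be included in NAJS, and the window will differ from the treatment end used for restart and switch. Showing both counts makes that visible.
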